October
2025

Women Supporting Women Using Local Solutions to Improve Infant and Young Child Feeding and Care Practices in Punjab, Pakistan

STUDY PROTOCOL

Study Overview

JUSTIFICATION.

This study responds to a call by the Pakistani government and public health researchers who have identified combatting child malnutrition as a high priority for Rahim Yar Khan (RYK) district in the province of Punjab. This study will focus on the proximal causes of malnutrition (inadequate diet and infections).

GOAL.

To rehabilitate moderately malnourished children 7-23 months of age and enable mothers to sustain this healthy growth at home by changing their infant and young child feeding (IYCF), care, hygiene, and health-seeking behaviors.

PURPOSE.

The OVERALL STUDY PURPOSE is to develop and evaluate a behavior change educational program to prevent malnutrition in the province of Punjab, Pakistan. The study has two main phases: the Formative Research Phase and the Intervention Phase.

The PURPOSE OF THE FORMATIVE RESEARCH is to identify uncommon but successful (i.e. *Positive Deviant*) IYCF behaviors practiced by local mothers of well-nourished children from economically disadvantaged homes, and to develop an education program informed by these best-practices and WHO guidelines.

The PURPOSE OF THE INTERVENTION PHASE is to deliver the educational program to mothers with undernourished children in the Intervention arm of the study who are equally disadvantaged, and to evaluate its impact on the growth of children.

STUDY HYPOTHESIS.

The primary hypothesis is that a higher proportion of Index children in the intervention compared to the control group will experience an average weight gain of 400g/month in the first 4 mos of the intervention.

STUDY OBJECTIVES.

1. Understand local perceptions, experiences, and cultural norms around IYCF practices and care,
2. Discover demonstrably successful IYCF behaviours and strategies using local resources,
3. Develop and implement a culturally appropriate and context-specific intervention,
4. Evaluate the intervention using two comparisons: (a) Within the intervention group: assess Index children's growth patterns and change in household behaviours/factors relevant to IYCF (e.g., knowledge, practice, beliefs and norms). (b) Intervention vs control group: compare average weight gain of Index children and household behaviours/factors relevant to IYCF (e.g., knowledge, practice, beliefs and norms)

Research Methods

IMPLEMENTATION OF THE INTERVENTION

SUMMARY

The project is now ready to move into the intervention, informed by the formative research phase, aligned with Objective #3. The intervention targets households with moderately malnourished children between 7 and 15 months of age, and will follow and support these households for a period of 6-months. Consent will be obtained from mothers via thumbprint or signature. Severely malnourished children, regardless of group, will be referred to local health facilities for care. Households in the control group will continue with their usual feeding and care practices.

This study is rooted in an asset-based approach grounded in the belief that in every community there are certain individuals whose uncommon behaviours enable them to find solutions to prevalent and seemingly intractable problems. The intent of the formative research phase supported by the CAC was to learn what is already possible within the community of Rahim Yar Khan and to amplify these strategies to the wider community during the intervention phase. The intervention comprises of two major components: community sensitization and a 28-day behaviour change period.

COMMUNITY SENSITIZATION OVERVIEW

The community sensitization events will be held in each intervention cluster. These events will introduce the project to local families about complementary feeding for children 6-23 months of age. These sessions will be delivered using town-hall format with small group activities. Key messages supported with visuals and print materials from the 28-day behavior change program (discussed below) will be shared with the larger community. The objective of the community sensitization programs is to create community awareness about the project, share best practices related to complementary feeding with the wider community with the hope this will promote community buy-in as well as community and neighborhood support for households participating in the 28-day change program.

28-DAY BEHAVIOR CHANGE PRACTICE PROGRAM OVERVIEW

Prior to recruitment and starting the 28-day behavior change program, each child will undergo a health check by a physician at the local health facility, including anemia screening, and ensuring they are up to date with all required immunizations.

The 28-day behaviour change practice includes two sequential parts. The first part consists of bringing mothers and their moderately malnourished child together in a home-like setting (the Hearth) for a period of 2-weeks to rehabilitate their malnourished child and learn improved feeding, hygiene, and caregiving practices. The Hearth sessions delivered over 14 days (6 hearth days plus 1 rest day/wk), and each session will last approximately 2.5 hrs. The second part consists of mothers practicing the learned behaviours in their home for another 2-weeks with support from the study staff. The Hearth/follow-up home visit model is based on the work of World Vision, which has shown that for some households, behaviour change, specifically in

feeding, caring, nurturing, and hygiene practices, may take up to 3 cycles to be fully adopted and for the child to regain a normal growth pattern. Hence, for children who do not reach their growth milestones after the first 28-day cycle, we will offer mothers the opportunity to participate in up to 3 cycles of the 28-day programs, with non-responders referred for medical evaluation. This length is deemed optimal to minimize dependency on the external rehabilitation process while allowing mothers the opportunity to “learn by doing”, and subsequently practice the new behaviours at home. The sessions will be facilitated by trained staff, and will emphasize practical learning, including preparing meals based on locally available foods.

Not all households will require 3 cycles; those whose children achieve the desired weight gain of 400 g (as recommended by WHO guidelines) may graduate earlier. This model is not intended to treat acute malnutrition or wasting but rather to address chronic malnutrition resulting from inadequate feeding and caregiving practices, which requires sustained engagement to reverse.

Following the hearth sessions, mothers will continue with a 14-day at-home practice period, during which they apply the newly learned behaviours in their household setting. Study staff will visit each home three times a week for 1.5 hours to reinforce behaviours, monitor child growth, and provide ongoing support.

If after each 28-day cycle the child meets their growth milestones, home visits will shift to monthly check-ins for up to 6 months. If the child falls short of meeting the growth milestone, families will be invited to repeat the 28-day Hearth and home practice cycles up to three times.

To reinforce the intervention, supplemental printed materials will be distributed to households during the 28-day program. These materials will be developed in collaboration with the CAC and based on findings from formative research. Designed to be accessible to illiterate populations, the materials will feature culturally relevant visuals with minimal text and be tailored for both men and women. An estimated 5,000 copies will be produced for dissemination to those participating in the 28-day behavior change program as well as the sensitization program.

EVALUATION

The project will evaluate the intervention’s effectiveness, study Objective #4. Evaluation tools have been adapted from existing validated instruments, informed by the formative research phase, reviewed by the CAC for clarity and cultural appropriateness and pilot tested. All tools have been translated to the local Punjabi dialect spoken by both Punjabi and Saraiki tribes residing in Rahim Yar Khan. Both the Treatment and Control Arm households will undergo the similar evaluations.

The evaluation will involve two major data collection strategies.

BASELINE AND FOLLOW-UP SURVEYS

Interview-assisted surveys will be conducted with mothers. These surveys will gather information on demographics, child health status, infant and young child feeding (IYCF) practices, hygiene behaviours, healthcare-seeking behaviours, gender norms, psychosocial factors, and available resources. Baseline surveys will be conducted after households have

consented to participate. Follow-up (Endline) survey will be conducted 6-months after the baseline surveys. With the exception of demographic information, which will only be obtained once at baseline, both baseline and endline surveys will obtain the same information. A third survey will be conducted 12 months post-intervention, if funding permits.

ANTHROPOMETRIC MEASUREMENTS (Weight and Height).

Anthropometric data will be collected by trained study staff to measure children's height and weight. Measurements will be taken with calibrated tools to minimize observer bias, and analyzed using WHO Anthro software to determine nutritional status based on standard Z-scores (weight-for-age, height-for-age, and weight-for-height). Children will be classified as underweight, stunted, wasted, or well-nourished. For the Treatment and Control Arm children, anthropometric measurements will be obtained at the time of recruitment, part of the baseline survey, during monthly follow-up, and part of the endline survey. Additionally, for the children in the Treatment Arm, weight will be collected during the 28-day behavior change practice program (Days 1, 13, and 28).

Inclusion Criteria

INTERVENTION PHASE

Eligible participants must meet all of the following conditions:

Child-Level Criteria:

- While children in the intervention phase will range from ages 7-23 months, At the time of recruitment children will range from Ages: 7–15 months.
 - Priority will be given to younger children, aged 7–11 months followed up by 12–15 months, to allow completion of the intervention and follow-up visits before the child turns 24 months of age, as complementary feeding refers to feeding practices between the ages of 6–24 months.
 - Moderate malnutrition, defined by: Weight-for-age Z-score between -2 and -3 standard deviations.

Household-Level Criteria:

- Households will be eligible to participate if:
 - They meet the classification of very poor or poor (based on community-defined wealth stratification).
 - Have access to clean water and sanitation.
 - Food secure at time of recruitment, defined as:
 - On government assistant program or at least one adult has permanent employment, or two or more have temporary employment.

- Ownership of at least one simple livestock (e.g., chicken, goat, or sheep).
- Access to a kitchen garden, or willingness to establish one with study support

Mother Eligibility Criteria:

The household is eligible only if the mother meets all of the following:

1. Mother is the primary caregiver for the Index Child (responsible for daily care, including supervision, bathing, and feeding).
2. Mother is alive and at least 18 years old.
3. Mother is currently breastfeeding the Index Child and willing to continue until the child reaches 2 years of age.
4. Mother expresses an interest in participating in the PD/Hearth program.
5. Mother agrees to attend up to three Hearth sessions.
6. Mother is willing and able to contribute to one of the following for Hearth sessions:
 - “Special” food items (e.g., apple, banana, carrot, chickpea, egg, garlic, lentils, rice, spinach, tomato, etc.), or
 - Other essential items (e.g., utensils, bowls, spoons, soap, nail cutter, towels, water, mat, salt, matchstick).
7. Mother provides permission for study follow-ups as outlined above.
8. Mother agrees to a full medical check-up for the Index Child at the nearest public health facility, including a one-time hematocrit finger-prick test (Hb test).
9. Mother provides informed consent via thumbprint or written signature.

Exclusion Criteria

Child-Level Exclusions:

- Children who are Severely malnourished, mildly underweight or of normal weight.
- Children with Physical disabilities: difficulty in seeing, hearing, picking up small objects with his/her hand.
- Children with chronic illnesses that may interfere with normal growth (based on past or current medical history):
 - Malabsorption
 - Chronic Kidney Disease
 - Inflammatory Bowel Disease
 - Congenital Heart Disease
 - Endocrine Disorders (e.g., hypothyroidism, growth hormone deficiencies)
 - Chronic Respiratory Diseases (e.g., asthma, lung diseases)
 - Congenital or Acquired Immunodeficiency, and Neurological Disorders

Household-Level Exclusion:

- Households who do not meet the inclusion criteria.

Recruitment Methods

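### The primary hypothesis cuts weight gain at 400 g/month, which keeps at most about 64% of the information in weights the trial already collects; a continuous, adjusted outcome would serve better

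*Protocol*

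**What the plan says.** The Study Hypothesis in the Study Overview makes the primary comparison one of proportions: a larger share of intervention than control children "will experience an average weight gain of 400g/month in the first 4 mos of the intervention". One gram value applies to every child.

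Two other places in the protocol speak of gain itself:

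- Study Objectives, 4(b): "Intervention vs control group: compare average weight gain of Index children".
- Recruitment Methods, Sample Size: 100 households per arm are said to give 80% power for a difference in child weight gain, with 400 g as the figure. No proportions, SD or alpha are given.

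The 400 g figure also serves as a programme milestone. In the overview of the 28-day program, "those whose children achieve the desired weight gain of 400 g (as recommended by WHO guidelines) may graduate earlier".

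The material for a continuous outcome is already planned. Weights are taken in both arms at baseline and monthly, and the anthropometric data are to be "analyzed using WHO Anthro software to determine nutritional status based on standard Z-scores", including weight-for-age.

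On age, the Inclusion Criteria state: "At the time of recruitment children will range from Ages: 7–15 months". They add: "Priority will be given to younger children". The arms are formed from different Union Councils, not by randomisation.

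**The concern.** A cut-off treats a child gaining 390 g/month like one who gained nothing, and a child gaining 410 g/month like one gaining 600. The primary test then uses only part of what was measured. The loss is smallest when about half the children reach the cut and grows quickly as the cut moves into the tail. The protocol does not say what share of untreated, moderately underweight children would average 400 g/month (1,600 g over four months), so it gives no assurance that the cut lies near the middle.

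At stake is the chance of showing a real benefit with about 100 children per arm. In addition, the primary hypothesis, Objective 4(b) and the sample-size paragraph do not clearly describe the same outcome.

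**Working it through.** **1. The plan's own figure.** The 100 per arm cannot be reproduced, because SD, alpha and event rates are not stated. With two-sided alpha 0.05 (assumed), 100 per arm and 80% power, the detectable standardised difference in means is d = 0.398 (t test; the normal approximation gives (1.96 + 0.842) × √(2/100) = 0.396).

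- Read as a mean difference of 400 g, this implies an SD of 400/0.398 ≈ 1,005 g.
- Read as proportions, 100 per arm detects for example 10% vs 25%, 20% vs 38%, 30% vs 49% or 50% vs 69%.

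The paragraph does not say which is meant.

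**2. Information kept by a cut.** For a normal outcome cut at z, with p the share above it, the efficiency relative to comparing means is φ(z)²/[p(1−p)].

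- z = 0, p = 0.50: 0.3989²/0.25 = 0.637
- z = 1, p = 0.159: 0.2420²/(0.159 × 0.841) = 0.439

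The maximum is at p = 0.50, so the loss is at least 36% wherever 400 g falls. No growth table is needed for this.

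**3. Power from the same children.** Suppose the mean comparison has 80% power (d = 0.398, even shift). For each control share p₁, the intervention share is p₂ = 1 − Φ(z − 0.398). With p̄ the average of the two,

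power ≈ Φ{[p₂ − p₁ − 1.96√(2p̄(1−p̄)/100)] / √([p₁(1−p₁) + p₂(1−p₂)]/100)}.

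- p₁ = 0.500, p₂ = 0.655: (0.1547 − 1.96 × 0.0699)/0.0690 ≈ 0.26, power 60%
- p₁ = 0.159, p₂ = 0.274: (0.1150 − 1.96 × 0.0582)/0.0576 ≈ 0.02, power 51%

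| Controls reaching 400 g/month (assumed) | z | Information kept | Intervention share | Power, 100 per arm |
|---|---|---|---|---|
| 50% | 0 | 64% | 65.5% | 60% |
| 16% | 1 | 44% | 27.4% | 51% |
| 7% | 1.5 | 27% | 13.5% | 36% |
| 2% | 2 | 13% | 5.5% | 21% |

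The last two rows show how the loss grows in the tail; nothing in the protocol says the control rate is that low. Attrition and clustering by area are left out of both measures.

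**4. Does the cut also create bias from age mix?** Assume no treatment effect, mean gains of 350 and 250 g/month in children aged 7–11 and 12–15 months, within-band SD 100 g/month, 100 per arm, and no adjustment. The shares above 400 g are then 30.9% and 6.7%.

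- *70% vs 50% younger children.* Proportions: 0.7 × 30.9 + 0.3 × 6.7 = 23.6% against 18.8%, so 13% false positives. Means: a spurious 0.2 × 100 = 20 g/month with standard error 15.7, so 25%.
- *80% vs 40%.* Proportions: 26.0% against 16.3%, so 39%. Means: 40 g/month with standard error 15.5, so 73%.

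The unadjusted mean in grams is affected more than the proportion. What removes the problem is adjustment for age, or an age-standardised outcome, not the absence of a cut.

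**The case against.** A responder outcome is a defensible choice here. 400 g is the programme's own milestone, the proportion reaching it is easy to explain, and average gain is already compared under Objective 4(b). The information is therefore lost from the primary test, not from the study. This stands, and it is why the point is an improvement rather than an error that invalidates the trial.

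The power figures are relative. They start from an assumed 80% for the mean comparison and from unknown control rates. They also assume an even shift, whereas the programme repeats cycles for children below 400 g. If its effect is concentrated near the cut, the loss would be smaller. This too stands.

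A reader might make two stronger inferences that the protocol does not support:

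- *That the trial is shown to be underpowered.* The sample-size wording can be read as taking 400 g as the responder threshold, in which case its 80% may already refer to proportions. With no inputs stated, no absolute shortfall can be demonstrated.
- *That the fixed cut lets a difference in age mix pass as a treatment effect.* Step 4 shows that the cut is not the cause. The imbalance is also assumed: the protocol states one age range and one younger-first priority, with no different rule for controls. At a 10-point imbalance the false-positive rate for the proportion is only about 5–10% under the assumptions tried. Adjustment for age and sex may also be laid down in an analysis plan that is not at hand.

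**Conclusion.** The point holds as one of efficiency and consistency. The primary hypothesis fixes a dichotomised outcome where an objective already names the continuous one and the weights are already collected. Given normal gains and an even shift, the cut keeps at most 64% of the information. An 80% power for means becomes about 60% at best, and about 51% if 16% of controls reach the cut.

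An analysis plan cannot recover this while the protocol's primary outcome remains a proportion. Age mix between the non-randomised arms is no argument against the cut; it is only a reason to choose the adjusted or Z-score form of the continuous outcome. Neither form removes other differences between the areas.

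**What to change.** In the Study Hypothesis, make the primary outcome one of the following, compared between arms:

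- change in weight-for-age Z from baseline to month 4; or
- weight gain from baseline to month 4, adjusted for baseline weight, age and sex.

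Keep the proportion averaging 400 g/month as a secondary outcome with the same adjustment. Word Objective 4(b) and the sample-size paragraph to match, and state the SD and alpha behind the 100 per arm.

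The cost is protocol wording. Weight-for-age Z needs only weight, age and sex, so no new measurement is required. The headline becomes an adjusted mean difference rather than a simple proportion, which is somewhat harder to explain; the secondary outcome still reports the programme target. No graduation rule or other clinical rule is changed.

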Anthropometric Assessment. Each Index Child's weight and height will be measured at the start and end of each hearth session, and at the end of the 2-week home visits (Day 1, Day 13, Day 27 of each cycle). If, by the end of the cycle, the child has not gained at least 400g, they will be invited to repeat the cycle—up to a maximum of three cycles. Children failing to any gain weight between cycles will be referred to a public health facility for medical evaluation. Z-Scores will be calculated to quantify the child's nutritional status. Mid-Upper Arm Circumference (MUAC) will be taken to assess for wasting. During the follow-up period, the child's weight will be monitored monthly for up to six months post-intervention.

Health assessment.

Baseline health assessments will be conducted at local public health facilities within two weeks prior to the first Hearth session for participants in the treatment arm. Each Index Child will receive a full medical examination by a physician, a Hematocrit (Hb) test via finger prick, and verification and updates for routine immunizations.

All children showing "failure to thrive" (e.g., no weight gain or weight loss after a Hearth cycle) will be referred for medical assessment within five days, and accompanied by study staff.

Results of participants' health assessments will not be shared or retained by the research team. This assessment will be conducted solely to confirm that the child meets eligibility criteria and is well enough to participate in the 28-day behaviour change program. This information is sufficient for enrollment purposes, and no medical or health records beyond the anthropometric measurements will be collected, stored, or used as study data

Data collection

Data will be collected using structured tools and include:

Baseline and follow-up household surveys (at 6 months, and possibly 12 months post-intervention if funding permits): surveys will assess 24-hour food recall and indicators on feeding practices, WASH, gender roles, and health-seeking behaviour. Study survey instrument is attached to Section 9.5.

All data will first be recorded on paper and later digitized by trained personnel.

PROCEDURES FOR PARTICIPANTS IN THE CONTROL ARM

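### Practices under Objective 4 are described as mothers' interview answers, only one arm is coached on them, and nothing keeps a household's coaches from interviewing it, so over-reporting can read as behaviour change

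*Protocol*

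**What the plan says.** Study Objectives, item 4, sets two evaluations that include behaviour. Within the intervention arm the study will "assess Index children's growth patterns and change in household behaviours/factors relevant to IYCF". Between arms the text reads "Intervention vs control group: compare average weight gain of Index children and household behaviours/factors relevant to IYCF", with knowledge, practice, beliefs and norms given as examples.

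The Evaluation section states that "The evaluation will involve two major data collection strategies": surveys and anthropometry. On the first, "Interview-assisted surveys will be conducted with mothers". The Procedures for both arms add that "surveys will assess 24-hour food recall and indicators on feeding practices, WASH, gender roles, and health-seeking behaviour". On how the instruments were made: "Evaluation tools have been adapted from existing validated instruments, informed by the formative research phase", followed by review by the community committee, piloting and translation.

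On coaching, the 28-day programme overview says "Study staff will visit each home three times a week for 1.5 hours to reinforce behaviours", after 12 group Hearth days per cycle. Sensitization events are set for intervention clusters. Control households do not join the programme and keep routine care.

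The Consent Process section has staff conduct the baseline survey. No section says who conducts the endline survey six months after baseline, and none separates coaching staff from interviewing staff.

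**The concern.** A mother who has been taught what good feeding and handwashing look like knows which answer is expected, whether or not her practice has changed. A control mother asked the same question has not had that teaching. If treatment mothers over-report more, the difference in answers exceeds the difference in practice, and the error favours the intervention.

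The same error enters the within-arm change, because it arises after baseline. It would be stronger if the person asking is the person who taught, and the protocol leaves that open.

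At stake is the reading of Objective 4 for practices, and with it the mechanism in the Goal, where growth is to be sustained by changing behaviours. If reported practice improved and weight did not, the data could not show whether practice changed without effect or did not change at all. Analysis after the fact cannot recover practice that nobody observed.

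**Working it through.** **Side by side**

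| Element | Treatment arm | Control arm |
|---|---|---|
| Taught domains (Procedures, Group Hearth Sessions) | Complementary and active feeding, hygiene, caregiving, health-seeking | None from the study |
| Surveyed domains (Evaluation) | Include feeding practices, hygiene, care-seeking | Same |
| Group sessions | 12 per cycle × 1 to 3 cycles = 12 to 36 | 0 |
| Coaching visits | 3 per week × 2 weeks = 6 per cycle, so 6 to 18 | 0 |
| Source described for practices | Mother's interview | Mother's interview |
| Endline interviewer | Not stated | Not stated |

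The only measure stated against observer bias is calibrated tools, and it concerns anthropometry.

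**Timing.** Consent and baseline come 1–2 weeks before the first Hearth. One 4-week cycle then ends at about week 5–6. Three consecutive cycles end at about week 13–14 (1 + 12 to 2 + 12). Taking six months as 26 weeks, intensive coaching ends 12 to 21 weeks before endline (26 − 14 to 26 − 5), with monthly check-ins in between.

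**Illustrative size.** The protocol gives no power or prevalence figure for behaviours, so there is no figure of its own to reproduce. Its 100 households per arm, set for weight gain, is used here only as n. Everything else is an assumption: the same true prevalence p in both arms, a fraction o of non-practising mothers who report the practice, independent households, and a two-sided 5% test of two proportions.

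- Reported prevalence in an arm = p + (1 − p) × o.
- d = difference in reported prevalence; SE0 = √[2·p̄(1 − p̄)/n]; SE1 = √[(pC(1 − pC) + pT(1 − pT))/n].
- Probability of significance = Φ[(d − 1.96·SE0)/SE1] + Φ[(−d − 1.96·SE0)/SE1].

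Worked case: p = 0.30, o = 0.20 in the treatment arm and 0 in controls.

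- pT = 0.30 + 0.70 × 0.20 = 0.44, so d = 0.14 and p̄ = 0.37.
- SE0 = √(2 × 0.37 × 0.63/100) = 0.0683; SE1 = √[(0.2100 + 0.2464)/100] = 0.0676.
- (0.14 − 1.96 × 0.0683)/0.0676 ≈ 0.09, and Φ gives about 54%; the second term is negligible.

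Controls accurate, n = 100 per arm:

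| True p | o = 10%: gap, P(sig.) | o = 20%: gap, P(sig.) | o = 30%: gap, P(sig.) |
|---|---|---|---|
| 30% | 7 points, 18% | 14 points, 54% | 21 points, 86% |
| 40% | 6 points, 14% | 12 points, 40% | 18 points, 72% |
| 50% | 5 points, 11% | 10 points, 29% | 15 points, 57% |

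With 80 per arm and p = 40%, the three probabilities are about 12%, 33% and 63%.

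Controls also over-report, n = 100 per arm:

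| True p | Control 5%, treatment 10% | Control 10%, treatment 20% |
|---|---|---|
| 30% | 8% | 17% |
| 50% | 6% | 11% |

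With equal over-reporting in the two arms the probability is back at 5%. The differential between arms does the harm.

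**The case against.** The strongest case on the other side has five parts.

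- **The instrument is not shown.** It sits in Section 9.5 and may contain items that the interviewer observes. This stands: a reader might infer that practices rest solely on self-report, but the text at hand shows only that no other source is described.
- **The interviewers are not known to be the coaches.** This stands too. Staff conduct the baseline survey and endline is unassigned. A reader might infer that mothers will be interviewed by those who taught them; the protocol does not say so. The defect is that it does not rule this out.
- **Coaching largely ends three to five months before endline.** True, and it may weaken the effect. It does not remove it, since the taught answers can be remembered and home contact continues monthly.
- **Much of Objective 4 can only be asked, and the primary outcome is measured.** Correct. Knowledge, beliefs and norms have no other source, and the primary hypothesis concerns weight. No mediation analysis is stated, so no formal result depends on the behaviour contrast.
- **This is a general limit of education studies that cannot be blinded, and interpretation may be left to the analysis plan.** Partly fair. But who interviews and what is observed are data-collection decisions, which belong in the Evaluation section and must be fixed before fieldwork. Adapting validated tools and piloting them address clarity and cultural fit, not over-reporting in one arm.

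**Conclusion.** The point holds for reported practices: feeding, hygiene and care-seeking. Differential over-reporting can pass for behaviour change in both the between-arm and the within-arm comparison, and the protocol sets no safeguard against it in the text at hand.

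The documents support the risk and its direction, not its size. The illustrative false-positive probability runs from about 6% to 86%, depending wholly on assumed prevalence and over-reporting, so it shows only that a large differential would matter. A reader might infer that over-reporting will produce a false behaviour effect, or that the trial's main result is compromised. Neither follows: no figure in the protocol bears on how much mothers over-report, and weight does not come from the mother's report. No change of sample size follows. The change is worth making because it is cheap and can only be made before the interviews.

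**What to change.** In the Evaluation section, under Baseline and Follow-up Surveys:

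1. Require that baseline and endline interviews in the treatment arm are done by existing field staff who do not run that household's Hearth sessions or home visits, with the same staff interviewing in both arms where feasible.
2. State that these outcomes will be concluded as reported practice, supportive of the weight result, and not as evidence of changed practice on their own.
3. If Section 9.5 holds no interviewer-observed items, add a few to the planned visits in both arms. Avoid soap and the child's bowl or spoon: these are among the items mothers may bring to the Hearth, so their presence may reflect participation. If observed items already exist, say so here.

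Agreement with child growth should not be used to validate reported behaviour, since behaviour is meant to explain growth.

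The cost is some rescheduling and travel, which needs planning because recruitment proceeds one Union Council at a time, plus a few checklist items and a more modest behaviour claim. The bias is only partly removed: a different interviewer still represents the same project.
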